11.3 Vital Signs

A listing for vital signs (heart rate (HR), respiratory rate, systolic and diastolic blood pressure (BP), temperature, and body weight) at each visit will be presented.

11.4 Electrocardiogram

A listing for electrocardiographic (ECG) parameters (HR, RR interval, PR interval, QRS interval, QT interval, and QTc) at each assessment time point will be presented. The QTc will be calculated using Fridericia and/or Bazett correction.

11.5 COVID-19

A listing of participants with visits impacted due to COVID-19 for the ITT population will be provided.

12.0 **Interim Analysis**

There is no interim analysis planned for this study.

13.0 **Determination of Sample Size**

The study is early terminated; and the original study primary objectives are no longer applicable. The original study design of this protocol is for those participants who screen failed either of the two pivotal registration studies (ie, Studies RLM-MD-01 and RLM-MD-02). The original study design was to achieve 600 participants from these screen failures (assuming approximately 2800 participants will be screened for the two pivotal studies together) who will be randomized in a 2:1 ratio (for Relamorelin vs Placebo) to this study. For the originally designed two primary endpoints (original protocol dated October 6, 2017, amendments #1 and #2 dated December 20, 2017 and March 29, 2018, respectively), 600 randomized participants would provide at least 90% power for both the 4-symptom composite DGSSS responder endpoint (assuming a placebo rate of 14% and a treatment rate of 35%) and the vomiting responder endpoint (assuming a placebo rate of 11% and a treatment rate of 26%). For the redesigned key efficacy endpoint, change from baseline in 4-symptom DGSSS composite score at Week 12 (Protocol amendment #3 dated April 29, 2019), the planned sample size of 600 participants would provide more than 90% power in detecting a clinical meaningful difference, assuming Relamorelin provides additional 3.8 points of improvement as compared to Placebo.

14.0 **Statistical Software**

Statistical analyses will be performed using version 9.4 (or newer) of SAS on a Linux operating system.

15.0 Data Handling Conventions

15.1 Analysis Weeks for Efficacy Analysis

Table below presents the analysis weeks assigned for the efficacy analysis of the participant daily diary data related to DGSSD.

Table 15.1.1–1 Analysis Week Windows for Efficacy Analysis

Period	Analysis Week	Begins^a	Ends^a
Pretreatment (Baseline ^b)	Week -2	Day -14	Day -8
	Week -1	Day -7	Day -1
Treatment	Week 1	Day 1, day of randomization	Day 7
	Week 2	Day 8	Day 14
	Week 3	Day 15	Day 21
	Week 4	Day 22	Day 28
	Week 5	Day 29	Day 35
	Week 6	Day 36	Day 42
	Week 7	Day 43	Day 49
	Week 8	Day 50	Day 56
	Week 9	Day 57	Day 63
	Week 10	Day 64	Day 70
	Week 11	Day 71	Day 77
	Week 12	Day 78	Day 84
	Week 21	Day 141	Day 147
	Week 22	Day 148	Day 154
	Week 23	Day 155	Day 161
	Week 24	Day 162	Day 168
	Week 33	Day 225	Day 231
	Week 34	Day 232	Day 238
	Week 35	Day 239	Day 245
	Week 36	Day 246	Day 252
Week 49	Day 337	Day 343	
Week 50	Day 344	Day 350	
Week 51	Day 351	Day 357	
Week 52	Day 358	Day 364	

a Relative to the date of randomization; Day 1 = the day of randomization.

b Baseline values for efficacy parameters will be derived as average of the two pretreatment weeks.

For the Double-blind Treatment Period, diary day is calculated as (diary date - date of randomization + 1). For the Pretreatment Period, diary day is calculated as (diary date - date of randomization).

15.2 Derived Efficacy Parameters

15.2.1 Weekly DGSSS

Weekly scores for nausea, abdominal pain, postprandial fullness, bloating, and vomiting severity will be the average of the corresponding nonmissing daily scores if a participant has at least 4 nonmissing daily scores during a week (See section 15.1 15.1 for definition of analysis weeks). Weekly score will be set to missing if there are less than 4 days with nonmissing diary data during a week.

Weekly DGSSS is derived as the sum of the weekly DGSSD items of nausea, abdominal pain, postprandial fullness, and bloating. The range of DGSSS is from 0 to 40 with 40 indicating the worst possible. If any one of weekly items of nausea, abdominal pain, postprandial fullness, and bloating is missing, then the weekly DGSSS will be set to missing.

If any of the weekly values during the Run-in Period (Week -2 and/or Week -1) is missing, baseline for the DGSSD items (nausea, abdominal pain, postprandial fullness, bloating, and vomiting severity) will be the average of the scores reported during the seven days -consecutive or not- preceding Day 1.

The Week 52 weekly average DGSSS is the average of the weekly DGSSS from Weeks 49 to 52.

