4.1 Clinical Hypotheses

The clinical hypotheses are:

DG participants receiving relamorelin compared to DG participants receiving placebo will experience greater improvement in DGSSS as measured by:

- The change from baseline to Week 12 weekly DGSSS, and
- The change from baseline to Week 52 weekly average DGSSS (defined as the average of the 4 weekly DGSSS from the 4 weeks prior to the Week 52 visit).

Baseline is defined as the average of the 2 average DGSSS from the 2-week placebo Run-in Period.

[figure not shown]
5 Study Design

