5.3 End of Study Definition

The end of the study is defined as the date of the last visit of the last participant in the study.

A participant is considered to have completed the study if he/she has completed at least 364 days of treatment, and the last visit (Visit 7). Independent of the end of study definition, all laboratory tests with values considered clinically significantly abnormal during participation in the study or within 30 days after the last dose of study treatment should be repeated until the values return to normal or baseline or are no longer considered clinically significant by the investigator or medical safety physician (MSP).

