10. Able to provide written informed consent (IC) prior to any study procedures and willing and able to comply with study procedures
Additional inclusion criteria for randomization after the 2-week, placebo Run-in Period:
11. Compliance with the entry of data into the hand-held electronic device on at least 10 of 14 days during the Run-in Period

12. Compliance with administration of SC twice daily injections, as evidenced by entries made by the participant using the electronic, hand-held device on at least 10 of 14 days during the Run-in Period
13. The average of the daily DGSSS from the 2-week, Run-in Period must be ≥ 12

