8.1 Discontinuation of Study Treatment

Discontinuation of study treatment also requires discontinuation from the study. The following criteria should be evaluated:

- Special attention should be paid to the appearance of abnormal laboratory test results suggesting severe, drug-induced liver injury (DILI). Discontinuation of study treatment for abnormal liver function should be considered by the investigator when a participant meets criteria for Hy's law (see Section [9.2.7.1](#) and [Appendix 6](#)) or if the investigator believes that it is in best interest of the participant.

- ECGs should be carefully analyzed for findings pointing to potentially important cardiac events. If a clinically significant finding is identified (including, but not limited to changes from baseline in QT interval corrected using QTcB or QTcF after enrollment, the investigator or qualified designee should determine if the participant can continue in the study and if any change in participant management is needed. Generally, a QTc value of > 500 msec or an increase from baseline of > 60 msec after start of study treatment should prompt discontinuation of the participant from the study. Review of the ECG printed at the time of collection must be documented. Any new clinically relevant finding should be reported as an AE.
- Female participants who become pregnant during the study must be discontinued from treatment immediately and withdrawn from the study. See Section 9.2.5 and Appendix 5 for further details regarding follow-up of the participant through the pregnancy.

See the SoA (Section 2) for data to be collected at the time of treatment discontinuation.

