9.1.1 Key Efficacy Assessment - DGSSD

[figure not shown]
The main efficacy assessment is the DGSSD, a 7-item, patient-reported diary designed to assess the severity of 6 core signs and symptoms of DG—nausea, abdominal pain, postprandial fullness, bloating, vomiting, and early satiety—and the frequency of vomiting episodes ([Appendix 13](#)). Participants will report their symptoms daily from Visit 1 to Visit 4 (Day 84) in the DGSSD. Thereafter, participants will report their symptoms daily for each of the 4 weeks preceding Visits 5, 6, and 7. DGSSD entries are to be made daily at the same time every evening on the electronic hand-held device throughout the Treatment Period. Planned periods for DGSSD entries are provided in the SoA ([Section 2](#)).

The severity of DG symptoms are assessed using a 0 to 10 numerical rating scale (NRS), on which 0 = “no” or “not at all uncomfortable” (ie, absence of the DG symptom) and 10 = “worst possible” or “most uncomfortable” (ie, worst experience of the DG symptom).

[figure not shown]
The overall assessment of the severity of non-vomiting symptoms is derived from the weekly DGSSS, as the sum of the weekly averages of the DGSSD items of nausea, abdominal pain, postprandial fullness, and bloating, calculated from a participant’s daily DGSSD responses.

The range of DGSSS is 0-40 with the worst possible DGSSS for the 4 DG symptoms being 40, and the best possible DGSSS being 0. Psychometric analyses have shown that a decrease in the DGSSS by ≥ 8 points and a decrease in individual symptom scores by ≥ 2 points is recognized as a clinically meaningful improvement in DG symptoms by affected patients ([Psychometric Evaluation, RTI Health, 2017](#)). Further psychometric analyses will be conducted to confirm the clinically meaningful thresholds for improvement.

Approval Date: 12-Feb-2021 17:35:16 (GMT)

Approval Date: 12-Feb-2021 17:35:16 (GMT)

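### Does the missing rule on how many of Weeks 49 to 52 are needed leave the Week 52 DGSSS summary undefined?

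*SAP*

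**What the plan says.** The Week 52 key endpoint is described in four places.

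- Protocol 4.1 calls it the Week 52 weekly average DGSSS, "defined as the average of the 4 weekly DGSSS from the 4 weeks prior to the Week 52 visit".
- Protocol Table 10-3 describes it as the change from baseline in the average over Weeks 49 to 52 and does not mention a visit.
- SAP 10.0 repeats the Table 10-3 description.
- SAP 15.2.1 gives the derivation: "The Week 52 weekly average DGSSS is the average of the weekly DGSSS from Weeks 49 to 52".

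SAP Table 15.1.1-1 sets the analysis weeks. Its footnote reads "Relative to the date of randomization; Day 1 = the day of randomization", and Weeks 49 to 52 run from Day 337 to Day 364. Collection is described by visit: in Protocol 9.1.1, after Visit 4, "participants will report their symptoms daily for each of the 4 weeks preceding Visits 5, 6, and 7".

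Protocol 10.3.2.2 leaves missing data to the SAP. SAP 15.2.1 covers days within a week ("Weekly score will be set to missing if there are less than 4 days with nonmissing diary data during a week"), items within the score (one missing weekly item makes the weekly DGSSS missing) and weeks within the two-week baseline (a fallback to the seven days reported before Day 1). It has no such rule for weeks within the Week 52 average.

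SAP 4.0 records early termination on 04 September 2020. SAP 10.0 limits the key efficacy endpoints to descriptive analyses, which SAP 4.0 says were added for posting on two registries.

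**The concern.** The SAP handles missingness at every level of the score except the last, and the last decides who has a Week 52 value. Protocol 4.1 can be read as needing all four weekly scores. The SAP sentence fits that, but it also fits an average of whatever weeks exist, down to one. Two programmers could follow the same text and post different Ns, means and SDs for a key endpoint.

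Partial blocks are foreseeable. Protocol 8.1 states "Discontinuation of study treatment also requires discontinuation from the study", so a participant who stops treatment a few weeks before the end has a truncated block, and termination by the sponsor could do the same to others. If only one week is needed, the Week 52 mean includes people who left before the Week 52 visit. If all four are needed, it drops people who finished the study but had one sparse diary week.

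The dates add a second doubt. If the diary block follows the actual date of Visit 7 while the analysis weeks are fixed from randomization, a late visit moves diary days out of the analysis weeks.

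**Working it through.** **1. Reproduce the SAP windows.** Week w runs from Day 7(w − 1) + 1 to Day 7w. Week 49 is Days 337 to 343 and Week 52 is Days 358 to 364, as in Table 15.1.1-1.

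**2. Which date anchor governs?** SAP 15.1 states that its windows apply to the DGSSD diary data, and SAP 15.2.1 refers back to 15.1 for its weeks. Protocol Table 10-3 and SAP 10.0 both name Weeks 49 to 52. Only the parenthesis in Protocol 4.1 refers to the visit. The anchor for the analysis is therefore fixed.

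**3. How far apart can the two anchors be?** Assume a full 28-day diary on Days V − 28 to V − 1, with Visit 7 on Day V, and apply the 4-day rule.

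| Visit 7 on Day | Diary days in Weeks 49, 50, 51, 52 | Valid SAP weeks |
|---|---|---|
| 362 | 7, 7, 7, 4 | 4 |
| 365 | 7, 7, 7, 7 | 4 |
| 368 | 4, 7, 7, 7 | 4 |
| 369 | 3, 7, 7, 7 | 3 |
| 375 | 0, 4, 7, 7 | 3 |
| 376 | 0, 3, 7, 7 | 2 |

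The two definitions use identical days when Visit 7 falls on Day 365. A visit within three days either side still gives four valid SAP weeks. The Schedule of Activities and its visit windows are not shown in the public copy, so how often visits fall outside that range is unknown.

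**4. Early leavers.** With a complete diary up to the last day, the fourth day of each week makes that week valid. A last diary day of 340 to 346 gives one valid week, 347 to 353 gives two, 354 to 360 gives three, and 361 or later gives four. The two readings differ for last diary days 340 to 360, a span of 360 − 340 + 1 = 21 days.

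If all diaries stopped on the termination date (an assumption; the documents do not say so), the dates are:

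- latest randomization with one valid week: 04 September 2020 − 339 days = 01 October 2019
- latest randomization with four valid weeks: 04 September 2020 − 360 days = 10 September 2019

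The affected participants would be those randomized from 11 September to 01 October 2019, again 21 days. Enrolment dates are not given, so this yields no headcount.

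**5. Diary gaps among those who reach Day 364.** Assume each day is completed independently with probability p. A week is valid with probability q = P(Bin(7, p) ≥ 4), and all four are valid with probability q⁴.

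| p | q | All four valid, q⁴ | Lacking four, 1 − q⁴ |
|---|---|---|---|
| 10/14 | 0.892 | 0.632 | 36.8% |
| 0.80 | 0.967 | 0.873 | 12.7% |
| 0.90 | 0.997 | 0.989 | 1.1% |

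The first row uses the randomization criterion in Protocol 6.1.2 ("Compliance with the entry of data into the hand-held electronic device on at least 10 of 14 days during the Run-in Period"). That is the minimum for entry, so treating it as everyone's average is a worst case among these rows. Even there, the chance that no week is valid is (1 − 0.892)⁴ = 0.00014, or 0.01%.

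**6. Effect on the posted mean.** Adding the partial-block participants shifts an arm's mean by f × (mean of partial-block participants − mean of full-block participants), where f is their share. The documents give neither f nor the difference, so no shift can be computed.

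**The case for a change.** The best argument for acting is that the SAP wrote a missing-week rule for the two-week baseline and none for the four-week endpoint. Its authors had the problem in view and left this case open. The endpoint is one of two key ones, its summary was added by this SAP amendment, and one sentence would close the gap at almost no cost. A rule chosen by the programmer once the data are in hand is also weaker than one written beforehand.

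Much of this stands. The rule is absent, the band of last diary days in step 4 is correct, and the Protocol 4.1 wording differs from the SAP windows without SAP 16.0 saying so.

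Three parts do not stand:

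- The documents do not disagree on the number of weeks. Both name four weekly scores and neither states a minimum.
- The date anchor is not open, for the reasons in step 2.
- The size is not shown. It rests on an eligibility floor used as average completion, independent days, an assumed diary stop date and visit windows that cannot be seen.

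The absent sentence would record a choice between two acceptable conventions; it would not correct a wrong one. Extra counts by reason would largely repeat SAP 7.0, which already gives completers and discontinuers by arm and lists discontinuers by reason. Protocol Section 8 already has sponsor termination as its own reason.

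**Conclusion.** No change is needed. On the number of weeks, this is a gap that an analyst fills sensibly: averaging the available valid weeks and requiring all four are both defensible, and each weekly score already has to pass the 4-day and four-item rules. On the dates, it is a loosely worded phrase in Protocol 4.1 beside an explicit definition in SAP 15.1 that matches Protocol Table 10-3.

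What can differ is which participants enter a descriptive mean, SD and N. Protocol Table 10-2 defines the N for change-from-baseline summaries as participants with values at both baseline and the analysis visit, so the number behind the mean is part of the planned output. No test or interval depends on the choice, and SAP 13.0 states that the original primary objectives no longer apply. The Week 12 endpoint is a single week with a stated rule, so the question does not touch it.

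Among those reaching Day 364, the two readings could differ for 1% to 37%, for daily completion between 90% and the run-in floor and with independent days. Early leavers add only those whose last diary day falls between Day 340 and Day 360. The conclusion rests on the SAP governing the posted analysis and on efficacy remaining descriptive. If the Week 52 endpoint were to carry a formal comparison, the missing minimum would matter more.

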15.3 Visit Time Windows for Safety Analysis

No analysis visit window is needed for safety parameters. The nominal visit or eCRF visit will be used for listings.

15.4 Repeated or Unscheduled Assessments of Safety Parameters

If a participant has repeated assessments before the start of double-blind treatment with investigational product, the results from the final assessment made before the date of the first dose will be used as baseline.

However, all post-baseline assessments will be used for PCS value determination, and all assessments will be presented in the data listings.

15.5 Missing Date of the Last Dose of Study Treatment

When the date of the last dose of the double-blind investigational product is missing, all efforts should be made to obtain the date from the Investigator. If it is still missing after all efforts have been made, the last diary date will be used as the last dose date.

15.6 Missing Severity Assessment for Adverse Events

If severity is missing for an AE that started before the date of the first dose of double-blind investigational product, an intensity of mild will be assigned. If severity is missing for an AE that started on or after the date of the first dose of double-blind investigational product, an intensity of severe will be assigned. The imputed values for severity assessment will be used for the incidence summary; the values will be shown as missing in the data listings.

15.7 Missing Date Information for Adverse Events

The following imputation rules apply to cases in which the start date is incomplete (ie, partial missing) for AEs.

Missing day and month

- If the year is the same as the year of the date of the first dose of double-blind investigational product, then the day and month of the date of the first dose of double-blind investigational product will be assigned to the missing fields.
- If the year is prior to the year of the date of the first dose of double-blind investigational product, then December 31 will be assigned to the missing fields.
- If the year is after the year of the date of the first dose of double-blind investigational product, then January 1 will be assigned to the missing fields.

Missing month only

- The day will be treated as missing and both month and day will be replaced according to the above procedure.

Missing day only

- If the month and year are the same as the month and year of the date of the first dose of double-blind investigational product, then the date of the first dose of double-blind investigational product will be assigned to the missing day.
- If either the year is before the year of the date of the first dose of double-blind investigational product or if both years are the same but the month is before the month of the date of the first dose of double-blind investigational product, then the last day of the month will be assigned to the missing day.
- If either the year is after the year of the date of the first dose of double-blind investigational product or if both years are the same but the month is after the month of the date of the first dose of double-blind investigational product, then the first day of the month will be assigned to the missing day.

If the stop date is complete and the imputed start date as above is after the stop date, the start date will be imputed by the stop date.

If the start date is completely missing and the stop date is complete, then the following algorithm is used to impute the start date:

- If the stop date is on or after the date of the first dose of double-blind investigational product, the date of the first dose of double-blind investigational product will be assigned to the missing start date.
- If the stop date is before the date of the first dose of double-blind investigational product, the stop date will be assigned to the missing start date.

16.0 **Changes to Analyses Specified in Protocol**

The study was early terminated and only an abbreviated study report will be applied to this study, for which only minimum efficacy analyses will be implemented. As such, this document is an abbreviated statistical analysis plan for only selected study disposition, demographics, safety parameters and selected descriptive efficacy analyses.

17.0 **References**

There are no references.

Electronic Signatures

User	Date	Justification
[REDACTED]	16-Dec-2020 01:23:35 (GMT)	Document Originator Approval
[REDACTED]	15-Dec-2020 20:23:50 (GMT)	Manager Approval
[REDACTED]	15-Dec-2020 20:29:15 (GMT)	Subject Matter Expert Approval
[REDACTED]	15-Dec-2020 21:16:33 (GMT)	Subject Matter Expert Approval
[REDACTED]	15-Dec-2020 21:51:48 (GMT)	Subject Matter Expert Approval

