9.2.1 Time Period and Frequency for Collecting AE and SAE Information

All AEs and SAEs will be collected from the signing of the informed consent form (ICF) until 30 days after the final visit in the study (Visit 7) or Early Termination Visit at the time points specified in the SoA (Section 2). For rollover participants, ongoing AEs from lead-in Studies RLM-MD-01 and RLM-MD-02, and new AEs that occur after the signing of the ICF for RLM-MD-04 are considered to be AEs in RLM-MD-04.

Medical occurrences that begin before the start of study treatment but after obtaining IC (informed consent) will be recorded in the AE section of the eCRF and will be considered pretreatment AEs.

All SAEs will be recorded and reported to the sponsor or designee within 24 hours, as indicated in [Appendix 4](#). The investigator will submit any updated SAE data to the sponsor within 24 hours of it being available.

Investigators are not obligated to actively seek AE or SAE in former study participants. However, if the investigator learns of any SAE, including a death, at any time after a participant has been discharged from the study, and he/she considers the event to be reasonably related to the study treatment or study participation, the investigator must promptly notify the sponsor.

The method of recording, evaluating, and assessing causality of AE and SAE and the procedures for completing and transmitting SAE reports are provided in [Appendix 4](#).

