An AE will be considered a treatment-emergent adverse event (TEAE) if the AE began or worsened (increased in severity or became serious) on or after the date of the first dose of double-blind study intervention. However, an AE that occurs more than 30 days after the last dose of study intervention will not be counted as a TEAE. Per case report form instructions, a new AE record will be created with a new AE onset date for any AE that worsens. Therefore, TEAEs can simply be identified as those AEs with recorded onset date on or after the date of the first dose of double-blind study intervention and within 30 days of the last dose of double-blind study intervention.

An AE will be considered a treatment-emergent SAE (TESAE) if it is a TEAE that also is an SAE.

The number and percentage of participants with TEAEs, death, TESAE, treatment related TEAE, TEAEs leading to treatment discontinuation, and TEAEs leading to discontinuation from study will be presented by treatment group.

The number and percentage of participants reporting TEAEs in each treatment group will be tabulated by descending percentage in Relamorelin group, by system organ class (SOC), preferred term, and severity. If more than 1 AE is coded to the same preferred term for the same participant, the participant will be counted only once for that preferred term using the greatest severity for the summarization by severity.

The number and percentage of participants reporting treatment-related TEAE, TESAEs, treatment related TESAE, and having TEAEs leading to discontinuation of the study in each treatment group will be summarized by system organ class and preferred term.

In addition, listings for participants who died, participants with AEs, participants with TESAEs, participants with TEAEs leading to discontinuation from study will be presented.

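### SAP 15.7 has no rule for an adverse event with an unknown start and no complete stop date, and it ignores partial stop dates

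*SAP*

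**What the plan says.** SAP 15.7 handles incomplete AE start dates in three parts.

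- **Partial start.** "The following imputation rules apply to cases in which the start date is incomplete (ie, partial missing) for AEs". These rules look only at the known year or month relative to first dose. For a year-only start in the first-dose year, "then the day and month of the date of the first dose of double-blind investigational product will be assigned to the missing fields". None of them depends on the stop date.
- **Back-correction.** A start imputed under the partial-start rules is pulled back to the stop date, but only under this condition: "If the stop date is complete and the imputed start date as above is after the stop date".
- **Unknown start.** The only provision opens: "If the start date is completely missing and the stop date is complete, then the following algorithm is used to impute the start date". The start becomes the first-dose date if the AE stopped on or after first dose. Otherwise it becomes the stop date.

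No rule imputes or uses a partial stop date.

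SAP 11.1 defines a TEAE as an AE that began or worsened on or after first dose, with a limit of 30 days after last dose. It then makes this operational: "TEAEs can simply be identified as those AEs with recorded onset date on or after the date of the first dose". It does not say what happens when there is no onset date. TESAEs are the TEAEs that are serious.

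Events that precede dosing are in the same data. Under Protocol 9.2.1, medical occurrences after consent and before treatment "will be recorded in the AE section of the eCRF and will be considered pretreatment AEs".

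**The concern.** The TEAE flag depends on onset date, so a gap in the date rules becomes a gap in the flag. Two patterns go wrong.

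First, an AE with no start date that is ongoing, or has only a partial stop date, receives no date and cannot pass the onset test. This holds even if the partial stop (say, a month after first dose) shows that the AE was present on treatment. It also sits badly with the SAP's other conventions, which lean towards counting: an ambiguous same-year or same-month onset goes to first dose, and missing on-treatment severity becomes severe under SAP 15.6. That severity rule needs a start date too, so it is also undefined for these AEs.

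Second, an AE whose partial stop date lies wholly before dosing can be given a start on the day of first dose, after its own end.

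After termination, the TEAE and TESAE tables are a main by-arm safety output. The flag also feeds the summaries of treatment-related TEAEs and TEAEs leading to discontinuation, and the TESAE and discontinuation listings. A non-fatal serious event of unknown onset could be absent from both the TESAE table and the TESAE listing. Because the SAP is silent, two programmers could also produce different counts.

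**Working it through.** The plan states no figure to reproduce. The check applies 15.7 literally and then the 11.1 onset test. Illustrative assumptions: first dose 15 Jun 2020, and last dose on 4 Sep 2020, the termination date in SAP 4.0.

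| Start | Stop | Start date under 15.7 | TEAE under 11.1 |
|---|---|---|---|
| missing | 1 Aug 2020 | 15 Jun 2020 | yes |
| missing | ongoing or missing | none | cannot be flagged |
| missing | Aug 2020 | none | cannot be flagged |
| missing | May 2020 | none | cannot be flagged (ended before dosing) |
| missing | 20 May 2020 | 20 May 2020 | no |
| 2020 | ongoing | 15 Jun 2020 | yes |
| Jun 2020 | ongoing | 15 Jun 2020 | yes |
| Aug 2020 | ongoing | 1 Aug 2020 | yes |
| 2020 | 20 May 2020 | 20 May 2020 | no |
| 2020 | May 2020 | 15 Jun 2020 | yes, though it ended by 31 May |

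**Gap 1.** Rows 1 to 3 differ only in the stop date. A complete on-treatment stop yields a TEAE; an ongoing AE, or one with an August stop of unknown day, yields no date. Row 6 shows that knowing just the onset year is enough for an ongoing AE to be counted.

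**Gap 2.** The last two rows differ only in whether the day of stop is known. With the day, the back-correction works. Without it, the start stays at 15 June, 15 days after the latest possible stop (31 May).

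**Can the gap 2 pattern occur?** Protocol Appendix 9 gives a 4-week Screening Period and a 2-week Run-in: 4 + 2 = 6 weeks = 42 days. Counting back 42 days from 15 June 2020 gives 4 May 2020. AEs are collected from consent, so for a de novo participant an AE that ended between 4 and 31 May 2020 falls inside the planned collection window. An AE that ended well before that, such as in March, would predate consent and would not be an AE of this study. From the lead-in studies, only AEs still ongoing are carried in (Protocol 9.2.1). The pattern is possible but confined to a short interval.

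**The proposed rules on the same rows.** Missing start with an ongoing AE or an August stop: 15 Jun 2020, TEAE. Missing start with a May stop: 31 May 2020, not a TEAE. Start 2020 with stop May 2020: capped at 31 May 2020, not a TEAE. The other rows do not change.

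**The case against.** The strongest reply is that the gap is narrow and its consequence is not stated in the SAP.

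- A reader might infer that the 15.7 rules work only with a complete stop date, or that resolved AEs are kept and unresolved ones lost. The text does not support either. Every partial-start rule applies whatever the stop date, and an ongoing AE with a known onset year or month is dated normally. The loss needs a start date of which not even the year is known.
- A reader might also say that these AEs are excluded from the TEAE tables. The SAP does not say so. The definition in 11.1 turns on when the AE began or worsened, and the onset-date test is an operational shortcut. Strictly, the status is undefined. The general AE listing and the listing of deaths do not depend on the flag, so the record stays visible.
- Both patterns should be rare. AEs are collected prospectively, SAEs are reported within 24 hours, and AEs are followed to resolution or stabilization.
- The plan is abbreviated and its outputs descriptive. The rules are the same in both arms, and gap 2 errs towards over-counting.
- That early termination leaves more ongoing AEs, and so enlarges gap 1, is conjecture. Collection continues for 30 days after the Early Termination Visit.

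All of this limits the size and priority of the point. It does not supply the missing rule, and it does not make a start date after the known end of the event correct.

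**Conclusion.** The point stands as a minor correction. On their stated terms, the date rules leave one class of AE without a date and therefore impossible to flag: unknown start with a missing, ongoing or partial stop. They misdate another: year-only start in the first-dose year with a partial stop before first dose. The second is a wrong result from the stated rules, not just missing detail.

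The size cannot be computed. The documents give no rate of missing or partial AE dates, so the number of affected records is unknown, probably very small and possibly zero. Nothing in the documents suggests a difference between arms. The conclusion on gap 1 assumes that a programmer applies the onset-date test in 11.1 literally to a record with no onset date.

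**What to change.** Add two rules to SAP 15.7.

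(a) If the start date is completely missing and the stop date is missing, ongoing or partial, assign the first-dose date. There are two exceptions. If the known parts of the stop date lie before first dose, assign the last date compatible with them. If the AE is recorded as carried over from RLM-MD-01 or RLM-MD-02, do not apply the default, since its onset precedes dosing in this study.

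(b) Apply the back-correction to partial stop dates as well, so that an imputed start is never later than the last date compatible with the known stop month or year.

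The cost is two sentences and minor programming. Rule (a) may count a few more AEs of unknown onset as TEAEs in either arm, in keeping with the SAP's existing conventions.
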